3.1 General Design

This is a within subjects 2 x 2 design, in which all participants will experience all four conditions during four sequential weeks. Medication administered (Adderall vs. placebo) will be crossed with instructional set (truth vs. deception) and participants' performance on neurocognitive tasks will be compared across these groups. For example, participants will be told either accurately or inaccurately that they are receiving Adderall or placebo. This creates four conditions that will be delivered over four weeks (see table below). The presentation of these conditions will be counterbalanced across the four weeks for each of the participants, such that they will not

receive the same ordering of conditions.

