4.3 Study Recruitment and Screening

Advertisements posted around campus will include tear-off slips of paper with contact information. The study investigators have been able to recruit healthy controls in this age group in previous studies of a similar nature without going to TV or radio advertisements. A telephone pre-screen interview will be designed to capture the most obvious exclusion criteria so that potential screen failures can be eliminated prior to an office visit.

Self-referred potential subjects will have a pre-screen telephone interview. If self-referred potential subjects meet criteria from this pre-screen telephone interview, a screening appointment will be scheduled.

Screening Appointment (1-2 hours): During the consent process, the purpose of the study, its risks and benefits, the rights of the participants, and what will be required of participants will be discussed. The participants will be given time to ask questions and have their questions answered by trained research staff. A pregnancy test will be obtained for all non-sterile female participants and a urine drug screen will be obtained for all participants at the screening interview. Positive results on either will result in immediate disqualification from the study. Results will be read

prior to giving any medication to a subject. These procedures will not be repeated during the study unless considered clinically necessary based on history or signs and symptoms at the discretion of the study physicians. Participants will review the MRI safety questionnaire to ensure that it is safe for them to be scanned. Participants will then fill out a demographics sheet, MRI Safety Questionnaire, Prescription Stimulant Expectancies Questionnaire (PSEQ-II), and an ADHD screener, the Adult Self-Report Scale (ASRS) Symptom Checklist. Medical and psychiatric history will be reviewed. The absence of an ADHD diagnosis will be confirmed by a physician investigator.

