4.4 Early Withdrawal of Subjects

4.4.1 When and How to Withdraw Subjects

Students will be informed they may withdraw from the study at any time, for any reason, before it is completed. They will be informed that their participation will not affect their class standing or grades at UAB. They will not be offered or receive any special consideration if they take part in the research. Employees will be informed that taking part in the research is not part of their UAB duties and refusing to be a part of the study will not affect their job or relationship with UAB. They will not be offered or receive any special job-related consideration if they take part in this research.

5. Study Drug

Dextroamphetamine-amphetamine & Placebo

6. Study Procedures

Study Appointment (2-3 hours): Pulse and blood pressure will be measured before medication is administered. If pulse and blood pressure are within acceptable limits, medication will be administered. A potential side effect checklist (attached) will be reviewed after the period of time in which medication effects would become active. Any reported side effects will be addressed prior to continuation of the session. The MRI safety questionnaire will be reviewed and signed at each scanning visit. This questionnaire will be filed at the CINL. Any abnormal findings will be discussed with physician investigator who will determine if the subject is fit to participate in the study.

The participant will be given either a placebo or Adderall depending on randomization. Each participant (N = 4) will either be told that he/she is receiving Adderall or placebo, as indicated on pre-labeled medication bottles to preserve the double-blind nature of the study. The participant will either receive medication or placebo as they are informed, not receive medication when they believe they are receiving medication, or will receive medication when they believe they are not receiving medication. This will allow for measurement of expectancy, which is a core measure for this study. This study design makes the comparison of cognitive performance based on actual versus perceived benefit possible. Presented below is an example table of study conditions.

Conditions will be counterbalanced across participants to control for order effects.

	Week 1	Week 2	Week 3	Week 4	
Expecting	Adderall	Adderall	Placebo	Placebo	
Medication	Adderall	Placebo	Placebo	Adderall	

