(Expecting refers to whether participants are told that they are taking Adderall or a placebo pill. Medication refers to the pill that participants are actually receiving.)

Before the medication is administered and after the MRI scan, participants will complete the POMS (Profile of Mood States) to measure mood and euphoria (attached). Participants will also self-report on their perceived mental acuity pre-dose and after each cognitive task (described below) performed in the scanner on a scale of 0-100with 100 indicating "more sharp than normal."

Cognitive testing will be timed to begin 45 minutes after medication or placebo is given.

Participants will then start the magnetic resonance spectroscopy scanning portion of the session, which will take one hour. The MRI scan will not include the use of a contrast agent. A 3 Tesla Siemens Prisma scanner and 20-channel head coil will be used. Scan sequences are listed below:

- Auto-align scout (1 min): to determine brain orientation and slice prescription. Will use 260mm field of view (FOV), 160 x 160 matrix, 3.15ms repetition time (TR), 1.37ms echo time (TE), 1.6mm slice thickness, no gap. The scout data are not used in post-scan analyses, so processing and analysis steps are not described.
- T1-weighted magnetization prepared rapid gradient echo (MPRAGE) high-resolution scan (10 min): for anatomical localization and to achieve standard space for group analyses.
 Will use 230mm FOV, 256 x 256matrix, 2000ms TR, 2.51ms TE, 0.9mm slice thickness, and no gap, yielding 0.9x0.9x0.9mm voxels.
- Functional MRI (60 min): Axial T2*-weighted images will be acquired using an echoplanar sequence 220x220 FOV, 64x64 matrix, 2000ms TR, 28ms TE, 3mm slices, yielding 3x3x3 mm voxels. Heart rate and respirations will be measured continuously in the scanner.
 - Participants will complete a "resting state" scan in which they are instructed to close their eyes and rest.
 - While undergoing fMRI scans, participants will complete three different cognitive
 tasks measuring aspects of sustained attention, new learning, and working memory.
 Participants will receive a short explanation of each task, as well as sample items,
 prior to entering the scanner, and will be able to have their questions answered.
 Specific task instructions will also be presented on screen inside the scanner prior to
 each task.
 - The first task will utilize a paced serial addition paradigm. Participants will be

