After the MRI portion of the session is complete, an additional neuropsychological battery will be administered to participants:

Repeatable Battery for the Assessment of Neuropsychological Status (RBANS): Measures various domains including immediate and delayed memory, visuospatial/constructional, language, and attention

Debriefing: After all four weeks of the protocol, a research assistant will conduct the debriefing portion of the session to inform participants about the deception aspect of the study. Following a manipulation check, the research assistant will disclose whether the participant received Adderall or placebo during each session. The research assistant will discuss the participants' feelings

about the deception, use this as a chance to educate them about cognitive enhancers, and more fully explain the reasons for doing the study. Participants will be given as much time as deemed clinically appropriate to answer all questions and concerns or address any feeling of betrayal in an accepting way.

Prior to leaving, the side effect checklist will be completed a final time and blood pressure and pulse rechecked by trained study staff. Stable subjects will be allowed to leave. Any subjects experiencing side effects will be observed longer, or in the rare event of more moderate to severe adverse events (most commonly hypertension < 160/110), will be referred to the ER at the discretion of the physician and PI. Orange juice will be kept on site for use in subjects experiencing negative symptoms, as acidifying urine increases amphetamine excretion. A study physician will be available at all times.

7. Safety and Adverse Events

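### Is a manipulation check held only at the end-of-study debriefing too late for a trial that calls expectancy a core measure?

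*Protocol*

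**What the plan says.** Protocol Section 3.1 (General Design) sets out a within-subject 2 x 2 crossing of pill and instruction, in which "all participants will experience all four conditions during four sequential weeks". Section 6 (Study Procedures) describes how the told label is combined with the actual pill and then remarks: "This will allow for measurement of expectancy, which is a core measure for this study". The note under the table of conditions in that section defines the factor: "Expecting refers to whether participants are told that they are taking Adderall or a placebo pill".

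The only check named as a manipulation check is in the debriefing paragraph of Section 6. On timing: "After all four weeks of the protocol, a research assistant will conduct the debriefing portion of the session". On order: "Following a manipulation check, the research assistant will disclose whether the participant received Adderall or placebo during each session". The content of the check is not described.

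Other self-reports are planned. At screening (Section 4.3): "Participants will then fill out a demographics sheet, MRI Safety Questionnaire, Prescription Stimulant Expectancies Questionnaire (PSEQ-II), and an ADHD screener". In each session (Section 6), before dosing and after the scan, "participants will complete the POMS (Profile of Mood States) to measure mood and euphoria"; and "Participants will also self-report on their perceived mental acuity pre-dose and after each cognitive task", on a 0-100 scale. A side-effect checklist is reviewed once drug effects would be expected and is completed a final time before the participant leaves. It is an attachment that is not shown.

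The primary endpoint (Section 3.2) is feasibility and acceptability. The Study Summary plans 4 completers with 6 alternates, and Section 10 does not anticipate publication.

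**The concern.** A study of expectancy needs some assurance that participants believed what they were told. Here the label is set four times, in two of the four sessions it is false, and the named check comes once, at the end. Belief in sessions 1 to 3 would then be recalled, possibly coloured by later sessions. The one questionnaire on stimulant expectancies is listed only at screening, before any label is given. The acuity and mood ratings are not worded as responses to the pill.

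What would be at stake is the reading of a null result. If performance looked the same under both labels, the sponsor might be unable to tell an expectancy that has no effect from a label that nobody believed. One rating of pill effect per session seems a cheap remedy, and no later analysis plan could recover data that were never collected.

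**Working it through.** The Protocol gives no figure on this point to reproduce. The check is a set of counts and a comparison of the passages.

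1. **How much belief would be recalled.** Inputs: 4 completers (Study Summary) and 4 sessions each (Section 3.1), so 4 x 4 = 16 participant-sessions. Assume that the check asks about every session and that the debriefing closes session 4. Then 4 x 3 = 12 of 16 (75%) are recalled. With sessions exactly 7 days apart, the lags are 3 x 7 = 21, 2 x 7 = 14 and 1 x 7 = 7 days. No visit window is stated. If each session may fall on any day of its own week, the ranges are:
   - session 1: 22 - 7 = 15 to 28 - 1 = 27 days
   - session 2: 22 - 14 = 8 to 28 - 8 = 20 days
   - session 3: 22 - 21 = 1 to 28 - 15 = 13 days

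   The 75% is right under these assumptions, but since the check's content is not described, it is not a figure that the plan states.

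2. **What the expectancy comparison uses.** Section 6 defines the factor as the instruction given. The remark about a core measure follows directly on the description of told label crossed with actual pill, so it refers to that contrast and not to a questionnaire score. The label is assigned, and therefore known, in 16 of 16 sessions. Within each actual pill, each participant supplies one told-Adderall versus told-placebo difference: 2 x 4 = 8 differences. None depends on recalled belief.

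3. **What is already collected the same day.** Acuity is rated pre-dose and after each of three tasks: (1 + 3) x 16 = 64 ratings. The POMS is completed twice per session: 2 x 16 = 32. Each has a pre-dose value and can be set out by told label within actual pill, giving the same 8 differences per measure. The side-effect checklist, by its name and timing, also bears on response to the pill. Its content cannot be judged, so it cannot be said that nothing collected in the session concerns the pill.

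4. **What an added pill-effect rating would change.** It adds 1 x 16 = 16 ratings and 8 differences.
   - Recalled belief stays at 12 of 16, because an effect rating is not a belief rating: a participant may believe the label and still report no effect.
   - Placed last, after the tasks and the RBANS, it is at least as open to perceived performance as the acuity ratings.
   - Each participant is told placebo in 2 of 4 sessions. Asking then how much effect the pill had may invite doubt about later labels.

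5. **What 4 completers could show.** With 4 differences per pill, the smallest two-sided sign-test p is 2 x 0.5^4 = 0.125. Even for a direct belief question answered favourably by 4 of 4, the exact two-sided 95% lower limit is 0.025^(1/4) = 39.8%. For 16 of 16 it is 0.025^(1/16) = 79.4%, which treats sessions as independent and is therefore optimistic. Neither approach could settle the null-result ambiguity.

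**The case for a change.** The strongest opposing case is that a feasibility study is the right place to learn whether a repeated deception holds. A participant told placebo but given the drug may notice effects that day and doubt the label, and three weeks later that doubt may be misremembered. One neutrally worded item at the end of each session costs almost nothing, would be compared with the actual pill held constant, and would keep something from people who leave early, for whom no check is stated.

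Part of this stands. Same-day evidence is less prone to recall error than an end-of-study question, and acuity and mood are only indirect evidence that the label took. An investigator could reasonably choose to add such an item. But the item proposed is also indirect and shares the weakness held against the acuity ratings. Someone who leaves early does not provide all four conditions, and six alternates are planned.

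It is also true that the debriefing text does not say whether the check precedes the first mention of deception, or whether it covers each session in turn. It does place the check before the pills received are disclosed. The rest is procedural detail of a check whose content is not described; nothing in the text contradicts a sound order.

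**Conclusion.** The concern does not hold. The Protocol neither contradicts itself nor fixes the check badly. Expectancy is operationalised as the assigned label, known in all 16 participant-sessions. The belief check is supporting information, and holding it until the deception is complete is defensible. Its cost is recall for 12 of 16 sessions (75%), assuming that it covers every session and that the debriefing closes session 4. An added pill-effect rating would not lower that number, would overlap with 64 acuity and 32 POMS ratings already planned, and would carry some risk to the manipulation itself. With 4 completers, description only, a feasibility and acceptability endpoint and no anticipated publication, any gain is negligible. Experienced statisticians could differ on whether to add the item; leaving it out is not an error.

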Neuroimaging the Expectancy versus Pharmacotherapy Effect of Adderall on Cognitive Performance

Study Protocol

NCT03603028

May 15, 2019

[name], Principal Investigator University of Alabama at Birmingham Birmingham, AL 35294

Neuroimaging the Expectancy versus Pharmacotherapy Effect of Adderall on Cognitive Performance

Primary Investigator:

[name]
The University of Alabama at Birmingham
[name]
[contact]

[contact]

Study Summary

Title Neuroimaging the Expectancy versus Pharmacotherapy Effect of						
	Adderall on Cognitive Performance					
Methodology	Double blind, within subjects, balanced placebo, randomized controlled clinical trial.					
Study Duration	Estimated duration for the main protocol (e.g. from start of study to finishing the study) is approximately 1 year.					
Study Center(s)	The University of Alabama at Birmingham – Highlands Hospital and the Sparks Center, Birmingham, AL					
Objectives	To further explore the relationship between stimulant medication and its effect on cognitive function, specifically whether participants' expectations regarding the benefits of stimulant medication affects their performance on neurocognitive tasks.					
Number of Subjects	10 (4 to complete the study, and 6 alternate participants).					
Diagnosis and Main Inclusion Criteria	Inclusion Criteria - Age (18-24) - College student with at least average IQ - Willingness to standardize caffeine intake to 100mg on day of study Exclusion Criteria - Diagnosis of ADHD - Unwillingness to comply with caffeine specifications - Regular use of Adderall - Pregnant/breastfeeding - History of substance use disorders - Illicit stimulant use within the last year - Contraindications to stimulants (i.e., tics, Tourette's, cardiac disease, hypertension) - Uncontrolled medical illness - Active contagious infection					
Study Product, Dose, Route,	Study Product: Dextroamphetamine-amphetamine & Placebo, Dose: 10mg					
Regimen	Route: Oral Regimen: One dose in the AM at Imaging visits					

1. Introduction

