7.1 Definitions

Participants can experience adverse reactions to Adderall during the treatment. However, they have been screened carefully by experienced clinicians for the likely psychiatric and medical problems that lead to Adderall drug reactions, so severe reactions are very unlikely. Also, 10mg of Adderall is a standard adult starting dose, routinely and safely used in clinical practice. This dose is generally very well tolerated among most people. If participants do experience side effects they are likely to be mild and short—lived. This drug is very safe under medical supervision and more common side effects are generally mild.

Use of Adderall is associated with side effects such as:

- nervousness
- difficulty falling asleep or staying asleep
- dizziness
- nausea
- vomiting
- loss of appetite
- stomach pain
- diarrhea
- heartburn
- dry mouth
- headache
- muscle tightness
- drowsiness
- uncontrollable movement of a part of the body
- restlessness
- numbness, burning, or tingling in the hands or feet
- decreased sexual desire

The following are rarer but serious toxic effects from Adderall:

- fast, pounding, irregular heartbeat
- chest pain
- shortness of breath
- excessive tiredness
- slow or difficult speech
- fainting
- weakness or numbness of an arm or leg
- seizures
- changes in vision or blurred vision
- agitation
- believing things that are not true
- feeling unusually suspicious of others
- hallucinating (seeing or hearing voices that do not exist)
- motor tics or verbal tics
- depression
- · abnormally excited mood
- mood changes
- erection that lasts longer than 4 hours that could result in penile injury (sexual activity is discouraged until evening time when medications should be largely excreted)
- numbness, pain, or sensitivity to temperature in the fingers or toes
- skin color change from pale to blue to red in the fingers or toes
- unexplained wounds on the fingers or toes
- fever
- hives
- rash
- blistering or peeling skin
- itching
- · swelling of the eyes, face, lips, mouth, tongue, or throat
- hoarseness
- difficulty breathing or swallowing

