7.2 Recording of Adverse Events

All adverse events that occur in the course of the study will be documented in the research record. Further, all adverse events will be compiled and reported in summary form on an annual basis to the IRB and at the conclusion of the study.

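### Both described uses of the side effect checklist fall inside the 2-3 hour visit, so sleep effects, and other events that start after departure, reach the adverse event summaries only if a participant volunteers them

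*Protocol*

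**What the plan says.** The Study Summary sets the regimen: "One dose in the AM at Imaging visits". Section 6 describes the visit: "Study Appointment (2-3 hours): Pulse and blood pressure will be measured before medication is administered". The pre-dose measurements are therefore part of the 2-3 hours.

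The checklist appears at two points in section 6. The first is after dosing: "A potential side effect checklist (attached) will be reviewed after the period of time in which medication effects would become active". The second is at the end: "Prior to leaving, the side effect checklist will be completed a final time and blood pressure and pulse rechecked by trained study staff". The next sentence is "Stable subjects will be allowed to leave". Participants with side effects at that point are kept longer.

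Section 7.1 lists "difficulty falling asleep or staying asleep" among the side effects. Among the rarer serious effects it lists an erection of more than 4 hours, with the note that "sexual activity is discouraged until evening time when medications should be largely excreted". Section 7.2 then says: "All adverse events that occur in the course of the study will be documented in the research record". These events are summarised for the IRB every year and at study end. Section 7.4 has the study physician on call during imaging sessions.

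**The concern.** The checklist is the only active collection of side effects that the protocol describes, and it stops when the participant goes home. At least one effect that the protocol itself expects belongs to the night after the dose. The next weekly visit, as described, starts with pulse and blood pressure, and its first checklist follows the new dose. No step is described that asks about the days in between, and no contact is described after the fourth week.

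Two things are at stake. First, a site that follows the text exactly could report few or no sleep effects because the schedule gave no occasion to ask, and a reader of the summaries could not tell this from good tolerability. Second, unprompted reporting is a poor substitute in this design. Participants are told, truthfully or not, that they have had Adderall or placebo, and debriefing comes only after all four weeks. Someone told placebo has less reason to connect a bad night with the pill, and so less reason to mention it. Reporting may then vary with the very factor that the study manipulates.

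**Working it through.** No power or error-rate figure is involved. The check is a timeline and a count.

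**Inputs from the protocol.** Visit length 2-3 h = 120-180 min, including pre-dose steps (section 6). Morning dose (Study Summary). Cognitive testing from 45 min after the dose and a scanning portion of one hour (section 6); the timed sequences listed there sum to 1 + 10 + 60 = 71 min. Duration in the definition of prolonged erection: 4 h = 240 min (section 7.1). Four participants to complete, four weekly sessions each (Study Summary, section 3.1).

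**Step 1: is the stated visit length plausible?** End of scan after the dose = 45 + 60 = 105 min, or 45 + 71 = 116 min. The protocol gives no time for the RBANS or the pre-dose steps. Assuming 20-40 min and 10-30 min, the visit runs from 105 + 20 + 10 = 135 min to 116 + 40 + 30 = 186 min. This is broadly consistent with 2-3 hours, though the document alone does not reproduce that figure.

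**Step 2: latest scheduled checklist after the dose.** Post-dose time = visit length - pre-dose time. The upper limit for a standard visit is 180 - 0 = 180 min. With 15-30 min pre-dose (assumption), the range is 120 - 30 = 90 min to 180 - 15 = 165 min.

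**Step 3: compare with the named effects.**

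| Effect in section 7.1 | When it can be recognised | Position relative to the last scheduled check |
|---|---|---|
| Disturbed sleep | the night after a morning dose | always after it |
| Erection of more than 4 h, onset during the visit | 240 min from onset | reportable at the exit check; longer observation is provided for |
| Erection of more than 4 h, onset after departure | after departure | missed |
| Loss of appetite and most other listed effects | can appear on site | can be captured |

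Even if onset coincided with the dose, the 4-hour point lies 240 - 180 = 60 min or more beyond a standard visit. For sleep, a dose between 08:00 and 11:00 (assumption) puts the last check no later than 11:00 to 14:00, which is 11 to 8 h before an assumed 22:00 bedtime. The conclusion for sleep does not depend on these clock times.

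**Step 4: how many sessions.** 4 participants x 4 sessions = 16. Each participant has two Adderall sessions, one told Adderall and one told placebo: 4 x 2 = 8 with Adderall, 4 under each instruction. For weeks 1-3, 4 x 3 = 12 sessions are followed by a visit at which a participant could volunteer something. The 4 week-4 sessions are not. How many of those 4 carry Adderall depends on the counterbalancing and is not stated.

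**The case against.** **The finding rests on silence.** The checklist is an attachment that is not shown, and consent and contact pages are not available. Look-back or sleep items may exist, and so may instructions to report problems from home. This stands as a limit: a reader might infer that delayed effects are never collected, and the documents do not support that. They support only that no such step is described. A look-back item on the checklist would, on the stated timing, first be asked after the next dose, and no later use of the checklist is described after week 4.

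**Section 7.2 is a recording duty.** It does not promise active questioning, and an event reported later would still be documented; section 6 also says a study physician is available at all times. This is correct. A reader might infer that section 7.2 is contradicted. It is not, but its completeness is left to unprompted reports.

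**The window is not a hard 3 hours.** Participants with side effects are observed longer, so an erection that starts on site need not be lost. This stands, and narrows that item to onset after departure.

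**The evening remark is not a clearance time.** It is an aside in a caution about sexual activity. A reader might infer that the protocol says the drug clears only by evening, but the text does not go that far, and nothing here relies on it.

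**The stakes are small.** This is a four-person feasibility study with single 10 mg doses and no publication anticipated, and the primary endpoint does not mention tolerability after the visit. That limits the consequences, but the IRB summaries are still a stated output, and a bad night after each session may bear on acceptability.

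**A look-back could cue participants.** Asking about stimulant effects might lead someone told placebo to suspect drug. The checklist is already used within each visit under every instruction, so the added cue is slight.

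**Another reading of the exit check.** Because that paragraph follows the debriefing text, it could be read as applying only to the last session. That would make collection thinner and would not answer the point.

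**Conclusion.** The point holds in a limited form. As described, scheduled questioning about side effects ends when the participant leaves, at most 180 min after dosing in a standard visit. Disturbed sleep necessarily falls after that check in all 16 planned sessions (8 with Adderall), and a prolonged erection is missed when it begins after departure. For these effects the section 7.2 summaries depend on unprompted reports, which may differ between instructions. That difference is a reasoned possibility; the documents give no figure for it.

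A reader might extend the gap to loss of appetite and the rest of the list. The documents do not support this, because most of those effects can appear and be reported on site.

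The conclusion assumes four completers and that the unshown checklist and participant materials contain no look-back procedure. It does not depend on any assumed clock time. It is worth correcting, but it is not a flaw that invalidates the study.

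**What to change.** Reconcile sections 6, 7.1 and 7.2 on one stated adverse event collection window, as follows.

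- In weeks 2-4, complete the existing checklist before dosing, looking back to the previous session and including that night. Use identical wording whatever the participant was or will be told.
- After week 4, ask the same items in one brief phone or e-mail contact per participant.
- Count each event in the section 7.2 summaries under the session that preceded it.
- If debriefing has already taken place, flag week-4 answers as collected after unblinding.

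This proposes no rule on whether the next dose is given.

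Cost: about 5 minutes at each of three visits already scheduled (4 x 3 = 12 look-backs, about 60 minutes in total) and 4 short contacts, with no new instrument or visit. Downsides: up to a week's recall, week-4 reports that may be unblinded and so not fully comparable with weeks 1-3, and a slight extra cue about stimulant effects. If the attached checklist or participant materials already contain such a look-back, stating it in section 6 and adding the contact after week 4 would be enough, provided that the look-back comes before the new dose.
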